3. PRIMARY AND SECONDARY VARIABLES

3.1 Efficacy variables

3.1.1 Primary efficacy endpoint

US FDA: The primary efficacy endpoint for the US is the mean change from baseline in Hb averaged over week 28 to week 52. A multiple imputation approach with analysis of

¹ Subject-level deviations refer to important protocol deviations that will cause subjects to be excluded from the Per Protocol set, and therefore all their collected data from analyses based on this population.

Visit-level deviations refer to important protocol deviations that will cause only some data for subjects to be excluded from analyses based on the Per Protocol set, while the subjects remain in the Per Protocol set given that they did not meet any subject-level deviations. Data to be excluded from the Per Protocol analyses could be either data from a certain date, at which the deviation was met for the first time, onwards to the end of the study, or data during a period defined by the start and end dates of the deviation.

covariance (ANCOVA) will be applied as a method to handle missing data. Details of the multiple imputation ANCOVA are provided in Sections 4.2.4 and 4.2.5.

Hb results obtained from the central laboratory will be used for all Hb efficacy analyses. Baseline Hb is defined as the mean of the three last central laboratory Hb values from the screening and randomization visits.

Hb values under the influence of a rescue therapy will not be censored.

EU health authorities: The primary efficacy endpoint for the EU health authorities is the mean change from baseline in Hb averaged over week 28 to week 36, without having received rescue therapy within 6 weeks prior to and during this 8-week evaluation period.

3.1.2 Hb related secondary efficacy variables

The Hb related secondary efficacy variables are:

- The EU primary endpoint as specified in Section 3.1.1 is the first secondary efficacy endpoint in the analysis for FDA
- Mean change in Hb from baseline to the subjects mean level between week 28 to week 52 in subjects with baseline high-sensitivity C-reactive protein (hsCRP) greater than the Upper Limit Normal (ULN)
- Proportion of total time of Hb ≥ 10 g/dL from week 28 to week 52. The proportion of total time will be computed as follows: For each subject, the recorded Hb values will first be linearly interpolated between measurements. The time this interpolated curve is ≥ 10 g/dL will be computed and subsequently divided by the time between the measurements at week 28 and week 52. Subjects without any Hb measurements from week 28 will not be considered for this variable.
- Proportion of total time of Hb within the interval of 10-12 g/dL from week 28 to week 52. The proportion of total time will be computed as follows: For each subject, the recorded Hb values will first be linearly interpolated between measurements. The time this interpolated curve is within 10-12 g/dL will be computed and subsequently divided by the time between the measurement at week 28 and week 52. Patients without any Hb measurements from week 28 will not be considered for this variable.

3.1.3 Lipid related secondary efficacy variables

To evaluate the roxadustat effect on lipids, the following variable will be evaluated

- Mean change from baseline in LDL cholesterol to week 24.

3.1.4 Rescue therapy related secondary efficacy variables

The need for rescue therapy will be evaluated as

- Time-to-first (and proportion of subjects who received) administration of red blood cell (RBC) transfusion as rescue therapy (rescue therapy guidelines are specified in the CSP, Section 7.7.4).

For analyses based on the Safety Analysis set, time to the event will be calculated as the number of days plus one between the day of first dose of study drug and date of the first occurrence of the event, or if no event has occurred before censoring, the date of censoring (see Section 4.1.1). For analyses based on the ITT analysis set, FAS and PPS, time will be calculated as the number of days plus one between the day of randomization and date of the first occurrence of the event, or if no event has occurred before censoring, the date of censoring.

3.1.5 IV iron related secondary efficacy variables

The use of IV iron will be investigated with the variable:

- Average monthly IV iron use per subject during, week 36 to EOS (monthly defined as a period of 4 weeks).

3.1.6 Exploratory variables

The exploratory variables are:

3.1.6.1 Hb related exploratory variables

Mean change from baseline in Hb, utilizing all Hb values from week 28 until the EOT visit. An imputation for mean change in baseline will only be applied for subjects with no Hb values from week 28 to the EOT visit.

- Time to achieving target Hb for anemic (Hb<10 g/dL at baseline) subjects not receiving ESA <= 4 weeks prior to randomization and were ESA-naïve or near ESA-naïve (no ESA use <=4 weeks prior to randomization). Time will be computed analogously as time to first rescue therapy. Target Hb is achieved when Hb level is within 10-12 g/dL at two consecutive measurements. This will be repeated for subjects with no ESA use <= 4 weeks prior to randomization.
- Proportion of ESA-naïve anemic patients achieved Hb response by Week 24 in the subset of patients who were anemic (Hb< 10 g/dL at baseline) and were ESA-naïve or near ESA-naïve (no ESA use <=4 weeks prior to randomization).

Hb response (Yes/No), where Yes is defined as:

- Hb \geq 11.0 g/dL and Hb increase from baseline by \geq 1.0 g/dL, for subjects with baseline Hb > 8.0 g/dL; or

- Hb increase from baseline by ≥ 2.0 g/dL, for subjects with baseline Hb ≤ 8.0 g/dL

at two consecutive visits [dates] (with available data) separated at least 5 days during the first 24 weeks of treatment without having received rescue therapy (RBC transfusion, ESA, or IV iron) prior to Hb response. The first date of the two consecutive visits will be used as the date of response. The second date of the two consecutive visits will be used when evaluating the presence or absence of rescue therapy.

- Percent of total patient exposure time with achieved Hb level <9 , $9-<10$, $10-<11$, $11-<12$, $12-<13$, ≥ 13 g/dL during treatment.

3.1.6.2 RBC transfusion related exploratory variables

- Number of rescue therapy treatments given, RBC transfusion per patient exposure year (PEY).
- Proportion of subjects with RBC transfusions during week 28 to week 52.

3.1.6.3 Quality of life related exploratory efficacy variables

European Quality of Life Questionnaire in Five Dimensions, Five Levels (EQ-5D-5L)

The EQ-5D-5L consists of the EQ-5D-5L descriptive system and the EQ visual analogue scale (VAS). The EQ-5D-5L descriptive system comprises 5 dimensions of health: mobility, self-care, usual activities, pain/discomfort, and anxiety/depression. Each dimension has 5 levels: no problems, slight problems, moderate problems, severe problems, extreme problems. The visual analogue scale records the respondent's self-rated health status on a graduated (0–100) scale, where the endpoints are labelled 'Best imaginable health state' and 'Worst imaginable health state' with higher scores for higher HRQoL. The EQ-5D-5L variables are:

- Change from baseline in EQ-5D-5L index value
- Change from baseline in EQ VAS

and will be computed according to the EQ-5D-5L documentation.

Results from the EQ-5D-5L questionnaire will also be summarized descriptively.

3.1.6.4 Hospitalization related exploratory variables

- Number of hospitalization(s) and number of days of hospitalizations per PEY.
- Number of days spent in Intensive Care Unit (ICU) per PEY.
- Proportion of subjects who are re-admitted to hospital within 30 days per PEY.

- Proportion of subjects who are re-admitted to hospital within 30 days due to heart failure per PEY following a preceding hospitalization due to heart failure.
- Proportion and number of on treatment days of hospitalization-free survival.
- Proportion and number of on treatment days of hospitalization-free, emergency room- free, and skilled nursing facility-free survival. Number of days spent in a Skilled Nursing Facility that follow hospitalizations per PEY, and the total number of days covering both hospitalizations and subsequent days in Skilled Nursing Facility.

3.1.6.5 Other exploratory variables

- Variables concerning serum iron profiles: Iron, TIBC, Ferritin and TSAT. Mean value at each time-point tested, and change from baseline.
- Variables concerning lipids: total cholesterol, high-density lipoprotein (HDL) and triglyceride: mean values and change from baseline at each timepoint tested; percent of subjects who achieved target LDL level <100 mg/dL, at each timepoint ; subgroup analyses on patients on statins and those not on statins
- Variables concerning heart rate and blood pressure: heart rate, systolic blood pressure (SBP), diastolic blood pressure (DBP) and mean arterial pressure (MAP).
- Variables concerning concomitant medication: Usage of statins and types of statins, initiation of ESA therapy post study drug discontinuation
- Change from baseline in hepcidin to week 24.

3.2 Safety assessments

Safety will be further assessed by evaluating the following:

- Occurrence of treatment emergent adverse events (TEAEs) and treatment emergent serious adverse events (TESAEs)
- Changes from baseline in vital signs and physical examinations.
- Mean change from baseline in clinical laboratory values.
- Occurrence of clinically significant changes from baseline in vital signs and ECG values.

3.3 Adjudicated CV Events Analyses for Safety Assessments

The CV events being analysed in the PSAP will be adjudicated by the Independent Event Review Committee (IERC) according to the IERC charter. The same adjudication committee will be used for all the phase 3 studies (FG-4592-064, 1517-CL-0613, FG-4592-063, and D5740C00002) in the CKD-NDD program. Analyses of these adjudicated events are described in a separate pooled analysis plan.

3.4 Treatment compliance

Subjects will be asked to return all unused study medication and empty packages to the clinic at each visit. The amount of dispensed and returned study medication will be recorded in the eCRF. The percentage treatment compliance will be calculated as:

$((\text{Overall amount of dose actually taken})/(\text{Overall amount of dose to be taken})) * 100\%$
Subjects taking $\geq 75\%$ and $\leq 125\%$ of planned study medication are considered to be compliant.

Compliance will be summarized as follows:

- Descriptive statistics will be summarized by the two treatment groups
- Percent compliance will be categorized according to the following three categories:
 - $< 50\%$ (significant drug non-compliance)
 - $\geq 50\%$, $< 75\%$, $> 125\%$ (moderate drug non-compliance)
 - $\geq 75\%$, $\leq 125\%$ (drug compliance)

4. ANALYSIS METHODS

Statistical analyses will be performed by IQVIA™ using SAS® Version 9.4 or higher and, where appropriate, additional validated software.

4.1 General principles

All study data will be listed by treatment group, centre, and subject number. Throughout subject data listings, figures and tables, treatment groups will be labelled as “Roxadustat” and “Epoetin alfa”.

Study Day will be listed in all data listings whenever an assessment date is presented. Study Day is a relative number, relative to the date of first dose of study drug. Week is also a relative number, relative to the number of weeks from the first dose of study drug. Study Days 1-7 is defined as Week 0, Days 8-14 as Week 1, etc. Clinical events and other variables reported after the EOT visit for a subject will not be included in the primary efficacy and safety

analysis. If collected, these events will be included in tables. Events that are recorded as beginning prior to the date and time of randomization will not be included in a listing.

In addition to specific analyses and presentations that are detailed in the following sections, results will be summarised using descriptive statistics, including the number of subjects (n), mean, standard deviation (SD), median and range (i.e. minimum and maximum) as appropriate. For categorical variables counts and percentage n (%) per treatment group will be presented. Summaries of continuous variables will be based on non-missing observations. For time to event data, the number and percentage of subjects recording the event will be summarised. Ninety-five percent confidence intervals will also be included where appropriate, as a measure of precision. Demographic characteristics, qualifying risk factors and other specific medical and surgical history will be summarised for the ITT analysis set using descriptive statistics. Mean Hb values over time will be graphically displayed and grouped by treatment.

Dates will be presented in the format YYYY-MM-DD.

When the last dose date is missing, it will be imputed as the earliest date of last drug dispense date + number of days of drug dispensed, date of death, date of EOT visit or date of EOS visit.

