3.9.3 Procedures for discontinuation of a patient from investigational product

Patients permanently discontinuing study medication should be given conventional therapy, if applicable, and should always be asked to continue the regular study visits as described below.

A patient who decides to discontinue study medication will always be asked about the reason(s) to discontinue study medication and the presence of AEs (if any). These data will be ascertained and documented by the investigator and recorded in the eCRF as appropriate. AEs will be followed up (see Sections 4 and 6.4); and the patient should return all study medications.

Discontinuation from study medication is not the same as complete withdrawal from the study (withdrawal of consent), which has a direct impact on the potential validity of all study data, and should be avoided wherever possible. It is essential to collect as much data as possible for all patients throughout the study and especially all potential endpoint events.

All discontinued patients unless consent withdrawal will be followed up for vital status and hospitalizations until study closure (see Section 3.9.3.2).

If the patient permanently discontinues study medication prior to closure of the study, there should be several different options for their continuation in the study as described below:

3.9.3.1 Patient agrees to undergo the Premature Treatment Discontinuation Visit and then continue in-person study visits

The patient agrees to undergo the Premature Treatment Discontinuation Visit (PTDV) and then continue in-person study visits according to plan. This is the **preferred** option and patients who discontinue study medication will always be asked if they agree to this approach. If agreed, as above, the patient will undergo their PTDV within 15 days after the study medication is stopped. The PTDV includes the same assessments as the EOT visit. The patient will continue attending subsequent study visits according to schedule (Table 1), or if needed with reduced frequency until end of study is declared (i.e., when the prespecified number of primary events has been reached). The patient will then return for their EOS visit **as soon as feasible**, but no later than 60 days after the study closure has been declared. It is essential that the patients attend the EOS visit in person whenever possible.

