4.1.1 Censoring

For analyses based on OT+7, subjects will be censored at 7 days after last intake of study drug, or the EOS visit, whichever is earliest.

For analyses based on OT+3, subjects will be censored at 3 days after last intake of study drug, or the EOS visit, whichever is earliest.

For analyses based on OT+0, subjects will be censored at last intake of study drug, or the EOS visit, whichever is earliest.

For analyses based on the ITT analysis set and FAS, subjects will be censored at their individual EOS visit, regardless of if they have discontinued study drug or not. Complete endpoint information will be pursued with every effort for all subjects, unless they exercise their right to withdraw consent. Subjects who withdraw consent will be censored at date of withdrawal of consent, and subjects who are lost to follow up (LTFU) will be censored at last available contact.

Subjects who withdraw consent and for whom only vital status (known to be alive at study closure, or date of death) may be obtained from public records, the occurrence of all components of the primary endpoint cannot be assessed, and will thus be censored at date of consent withdrawn for all analyses. However, the determination of all-cause death will utilize all publicly known mortality data, even that extending beyond date of consent withdrawal. The vital status information will be included in the analysis of all-cause death as a single endpoint, and in sensitivity analysis and tabulations. Similarly, complete information on the endpoint may not be obtained for subjects who are LTFU. Any such subject will be censored in the analysis at the last contact where all elements of the endpoint were assessed. A subject

will not be recorded as LTFU until the end of the study, after every allowable effort to get in contact has been made. Hence, it is anticipated that the number of subjects LTFU will be limited.

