4.3.8 Safety assessment analysis

The safety analysis will be performed using the OT+7. Safety variables include adverse events (AE), laboratory variables, vital signs, ECG variables and physical examinations. For each safety variable, the last assessment made on the screening visits or the randomization visit will be used as the baseline for all analyses, unless specified otherwise.

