4.3.8.1 Adverse events

Adverse events will be coded using the Medical Dictionary for Regulatory Activities (MedDRA) version 20.0 higher.

An AE (classified by preferred term) started during the treatment period will be considered a treatment-emergent adverse event (TEAE) if it was not present prior to the first dose of study medication. An AE that starts more than 7 days after the last dose of study medication will not be counted as a TEAE.

The number, percentage and percentage per PEY of subjects reporting TEAEs in each treatment group will be tabulated by system organ class and preferred term; by system organ class; by preferred term and by system organ class, preferred term, and relationship to study medication. If more than one event occurs with the same preferred term for the same subject, the subject will be counted only once for that preferred term using the most severe and most related occurrence for the summarization by severity and by relationship to the study medication. In addition to reporting TEAEs by number of subjects, the table by system organ class and preferred term will also be reported by patient years and event rates. Thus, allowing for potential systematic differences in mean exposure between the treatment groups. The event rate for a particular AE will be derived as the number of subjects with the AE, divided by total number of days at risk for the AE across all subjects in given group, multiplied by 365.25 multiplied by 100.

The distribution of TEAEs by severity and relationship to study medication will be summarized by treatment group.

The incidence of common ($\geq 5\%$ of subjects in any treatment group) TEAEs, common treatment-emergent serious AEs (TESAE), and AEs leading to discontinuation of study medication will be summarized by preferred term and treatment group, sorted in decreasing overall (across treatments) frequency. Moreover, TEAEs leading to hospitalization by system organ class and preferred term will be presented. In addition, related deaths and fatal SAEs (i.e., events that caused death) will be summarized separately by treatment group, system organ class and preferred term. TEAEs with outcome of deaths and TESAEs will also be presented for the ITT analysis set.

TEAEs and TESAEs by system organ class and preferred term will also be reported with OT+3 and OT+0.

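### SAP 4.1 cuts the primary efficacy and safety analysis at the EOT visit, contradicting the SAP's own rules that count safety data to 7 days after last dose and ITT/FAS data to EOS

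*SAP*

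**What the plan says.** SAP 4.1 (General principles) gives a blanket rule: "Clinical events and other variables reported after the EOT visit for a subject will not be included in the primary efficacy and safety" analysis. It then adds: "If collected, these events will be included in tables".

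The operative sections set different limits, and none of them mentions the EOT visit as a cut-off:

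- SAP 4.1.1, for OT+7: "subjects will be censored at 7 days after last intake of study drug, or the EOS visit, whichever is earliest". OT+3 and OT+0 follow the same pattern with 3 and 0 days.
- SAP 4.3.8: "The safety analysis will be performed using the OT+7".
- SAP 4.3.8.1: "An AE that starts more than 7 days after the last dose of study medication will not be counted as a TEAE". An event starting within those 7 days can therefore be a TEAE.
- SAP 4.1.1, for ITT and FAS: "subjects will be censored at their individual EOS visit, regardless of if they have discontinued study drug or not". SAP 4.3.2 runs the US primary Hb analysis on ITT.

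On the visits themselves, Protocol 1.4.3 and 4.2 and SAP 1.2.2 place the EOT visit after study closure, and SAP 1.2 puts EOS 4 weeks after EOT. A subject who stops drug early has a separate premature treatment discontinuation visit (PTDV) and is then asked to continue scheduled visits. Protocol 3.9.3.1 says of it: "The PTDV includes the same assessments as the EOT visit".

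**The concern.** Two programmers could each follow the SAP faithfully and build different datasets. One would stop at EOT under 4.1; the other would run to last dose plus 7 days, or to EOS, under 4.1.1. The SAP states no order of precedence.

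The consequence is clearest for safety. A subject treated until common close-out takes drug until about the EOT visit, so most of the 7-day tail lies after EOT. Under 4.1 that tail is lost. An early stopper's tail ends long before any close-out visit, so 4.1 leaves it whole. The length of the on-treatment window would then depend on whether the subject completed treatment. Completion may differ by arm: Protocol 3.9.2 lists the need for more than one ESA rescue cycle as a reason for permanent discontinuation in roxadustat-treated patients only. There is also a risk of mismatch within the AE rates. SAP 4.3.8.1 divides subjects with an event by days at risk, and 4.1 removes late events without saying whether the matching days are removed too.

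**Working it through.** The plan gives no figure on this point, so the check sets the cut-off rules side by side and counts days. The only nearby figure, at least 99% power with 600 subjects, is unaffected. It reproduces: 0.45 / (1.25 × √(2/300)) = 4.41; 4.41 − 1.96 = 2.45; power 99.3%.

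**Step 1: safety tail, subject dosed to close-out.** Let k be the days from last dose to the EOT visit. OT+7 and the TEAE rule keep 7 days after last dose. A cut at EOT keeps min(7, k) days, so 7 − min(7, k) days are in conflict. The same applies to OT+3 with 3 in place of 7.

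| k (days) | OT+7 tail left by 4.1 | OT+3 tail left by 4.1 | OT+0 | OT+7 days in conflict |
|---|---|---|---|---|
| 0 | 0 | 0 | 0 | 7 |
| 1 | 1 | 1 | 0 | 6 |
| 3 | 3 | 3 | 0 | 4 |
| 4 | 4 | 3 | 0 | 3 |
| 7 or more | 7 | 3 | 0 | 0 |

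At k = 0 the three sets are identical, and up to k = 3 OT+7 equals OT+3. The documents do not give k. The protocol synopsis spaces roxadustat doses 2 to 4 days apart, so for a subject still dosing three times weekly k of 0 to 4 is a reasonable assumption, giving 3 to 7 days in conflict. Less frequent dosing would allow a larger k and a smaller conflict.

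**Step 2: scale across the trial (assumptions).** Assume 1,000 to 1,400 of the approximately 2,000 subjects are dosed to close-out.

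- 7 days each: 1,000 × 7 / 365.25 = 19.2 person-years; 1,400 × 7 / 365.25 = 26.8.
- 3 days each: 1,000 × 3 / 365.25 = 8.2; 1,400 × 3 / 365.25 = 11.5.

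The range is about 8 to 27 person-years. As a share of one subject's exposure, assumed to be 1 to 4 years, 7 days is 7 / 365.25 = 1.9% down to 7 / 1,461 = 0.5%.

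**Step 3: primary Hb endpoint.** EOT to EOS is 28 days, which 4.1.1 includes for ITT and 4.1 excludes. If close-out falls at week c of a subject's treatment, the disputed interval is weeks c to c + 4. It overlaps weeks 28–52 only when c lies between 24 and 52. For c of 52 or later the overlap is zero. The one visit scheduled in that interval is EOS itself, at week c + 4, and it falls inside weeks 28–52 only when c is between 24 and 48.

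**Step 4: subjects who stop drug early.** On the protocol's definition the PTDV is not the EOT visit, so 4.1 does not cut their later scheduled Hb values.

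**The case against.** The best defence has four parts.

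- **Specific over general.** Section 4.1 is headed as general principles, while 4.1.1, 4.3.8 and 4.3.8.1 are explicit. A programmer would probably follow the specific rules. That is likely, but the SAP does not say so, and the sentence in 4.1 is itself a definite exclusion.
- **Nothing is lost.** Post-EOT events still go into tables. This stands and limits the harm: the conflict concerns what enters the primary efficacy and safety analysis, not whether the data are shown.
- **A narrow reading of safety.** The words may mean only the primary safety analysis, that is, adjudicated CV events. SAP 4.3.1 sends that analysis to the pooled plan. The reading is possible and would leave the TEAE tables untouched. The safety half of the sentence would then have nothing in this SAP to govern and should not remain there.
- **Small and bracketed.** TEAEs and TESAEs are also reported on OT+3 and OT+0, and a week is a small share of exposure. This stands as to size. But if 4.1 is applied, those alternative windows no longer contrast with OT+7 for subjects treated to close-out.

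A reader might infer something stronger: because the PTDV repeats the EOT assessments, it could be taken as the EOT visit, and 4.1 would then strip all off-drug Hb from an analysis labelled ITT. The documents do not support this. Sharing assessments does not make the two visits the same. The protocol ties EOT to study closure, keeps early stoppers on scheduled visits after the PTDV and then takes them to EOS. SAP 1.2 follows their Hb to EOS on ITT principles.

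**Conclusion.** The contradiction is real and lies in current SAP text. It does not depend on the change log, although SAP Table 4 suggests the cause: it records that censoring for the set then called FAS, since renamed ITT, moved from EOT to EOS. The sentence in 4.1 fits the older rule.

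For safety, 7 − k days per subject treated to close-out are counted by one rule and dropped by the other: 3 to 7 days if k is 0 to 4. With an assumed 1,000 to 1,400 such subjects, this is roughly 8 to 27 person-years, concentrated entirely in those who completed treatment. For the primary Hb endpoint the reach is narrow: the 4 weeks after close-out, and only for subjects closed out before week 52. The non-inferiority conclusion is not shown to be at risk, and no sample-size figure changes. The point is worth correcting because the rule is wrong as written and, in an open-label study, should be fixed before database lock.

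**What to change.** Delete the sentence from SAP 4.1 and let 4.1.1 govern. State there that the OT+7, OT+3 and OT+0 windows follow the last dose whatever the date of the EOT visit, with days at risk cut at the same point as events.

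If the intent was to keep Hb values taken at EOS after close-out from entering the week 28–52 mean, replace the sentence with one that says only that.

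As a safeguard, add that a PTDV is not an EOT visit for ITT and FAS, so scheduled Hb after early discontinuation is retained.

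The cost is two or three sentences in the SAP. No new data and no protocol amendment are needed.
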